8.1.5.6 Other allowed dose interruptions for Pembrolizumab

Dosing interruptions are permitted in the case of medical / surgical events or logistical reasons not related to study therapy (e.g., elective surgery, unrelated medical events, patient vacation, and/or holidays). Subjects should be placed back on study therapy within 3 weeks of the scheduled interruption, unless otherwise discussed with the Sponsor. The reason for interruption should be documented in the patient's study record.

8.1.6 Rescue Medications & Supportive Care for Pembrolizumab

Participants should receive appropriate supportive care measures as deemed necessary by the treating investigator. Suggested supportive care measures for the management of AEs with potential immunologic etiology are outlined along with the dose modification guidelines in [Section 8.1.5.5, Table 3](#). Where appropriate, these guidelines include the use of oral or IV treatment with corticosteroids, as well as additional anti-inflammatory agents if symptoms do not improve with administration of corticosteroids. Note that several courses of steroid tapering may be necessary as symptoms may worsen when the steroid dose is decreased. For each disorder, attempts should be made to rule out other causes such as metastatic disease or bacterial or viral infection, which might require additional supportive care. The treatment guidelines are intended to be applied when the investigator determines the events to be related to Pembrolizumab.

Note: If after the evaluation of the event, it is determined not to be related to Pembrolizumab, the investigator does not need to follow the treatment guidance. Refer to [Table 3](#) in [Section 8.1.5.5](#) for guidelines regarding dose modification and supportive care.

It may be necessary to perform conditional procedures such as bronchoscopy, endoscopy, or skin photography as part of evaluation of the event.

Note: In addition to [Table 3](#), supportive and treatment information may be found in the investigator brochure in the "Warnings and Precautions" section of the company core data sheet provided in the Appendix of that document and also provided in the product label.

8.1.7 Dose modification and toxicity management of infusion-reactions related to Pembrolizumab

Pembrolizumab may cause severe or life threatening infusion-reactions including severe hypersensitivity or anaphylaxis. Signs and symptoms usually develop during or shortly after drug infusion and generally resolve completely within 24 hours of completion of infusion. Dose modification and toxicity management guidelines on Pembrolizumab associated infusion reaction are provided in [Table 4](#).

Immune Design**G100 (GLA-SE) and Pembrolizumab or Rituximab****Protocol IMDZ-G142; Version 04B, November 15, 2018****Table 4: Pembrolizumab Infusion Reaction Dose Modification and Treatment Guidelines**

NCI CTCAE Grade	Treatment	Premedication at Subsequent Dosing
Grade 1 Mild reaction; infusion interruption not indicated; intervention not indicated	
 Increase monitoring of vital signs as medically indicated until the participant is deemed medically stable in the opinion of the investigator. 	None
Grade 2 Requires therapy or infusion interruption but responds promptly to symptomatic treatment (e.g., antihistamines, NSAIDs, narcotics, IV fluids); prophylactic medications indicated for ≤ 24 hrs.	
 Stop Infusion. Additional appropriate medical therapy may include but is not limited to: 
 IV fluids Antihistamines NSAIDs Acetaminophen Narcotics Increase monitoring of vital signs as medically indicated until the participant is deemed medically stable in the opinion of the investigator. If symptoms resolve within 1 hour of stopping drug infusion, the infusion may be restarted at 50% of the original infusion rate (e.g., from 100 mL/hr. to 50 mL/hr.). Otherwise dosing will be held until symptoms resolve and the participant should be premedicated for the next scheduled dose. 
Participants who develop Grade 2 toxicity despite adequate premedication should be permanently discontinued from further study drug treatment
	Participant may be premedicated 1.5h (\pm 30 minutes) prior to infusion of pembrolizumab with: Diphenhydramine 50 mg po (or equivalent dose of antihistamine). Acetaminophen 500-1000 mg po (or equivalent dose of analgesic).
Grades 3 or 4 Grade 3: Prolonged (i.e., not rapidly responsive to symptomatic medication and/or brief interruption of infusion); recurrence of symptoms following initial improvement; hospitalization indicated for other clinical sequelae (e.g., renal impairment, pulmonary infiltrates) Grade 4: Life-threatening; pressor or ventilator support indicated	
 Stop Infusion. Additional appropriate medical therapy may include but is not limited to: 
 Epinephrine** IV fluids Antihistamines NSAIDs Acetaminophen Narcotics Oxygen Pressors Corticosteroids Increase monitoring of vital signs as medically indicated until the participant is deemed medically stable in the opinion of the investigator. Hospitalization may be indicated. 
**In cases of anaphylaxis, epinephrine should be used immediately.
 
Participant is permanently discontinued from further study drug treatment.
	No subsequent dosing
Appropriate resuscitation equipment should be available at the bedside and a physician readily available during the period of drug administration. For further information, please refer to the Common Terminology Criteria for Adverse Events v4.0 (CTCAE) at http://ctep.cancer.gov		

8.1.8 Rituximab Background

In Part 5, patients will receive this anti-CD20 antibody in combination with G100 as an investigational agent for the treatment of follicular lymphoma. Rituximab is an approved standard treatment for follicular lymphoma patients: approved regulatory labeling and institutional guidelines for dose, administration including premedication, contraindications, warnings and precautions should be followed. Rationale for addition of rituximab and details of Part 5 design are described in [Section 4.1](#) and [6.1](#). Treatment regimen is presented in [Figure 9](#). Brief summary of administration, warnings and precautions is summarized below.

8.1.8.1 Rituximab Dose

Rituximab dose is 375 mg/m² as an IV infusion administered on Day 0 and then continued once weekly for 4 doses on a schedule as described in [Section 4.1](#) and [6.1](#) and [Figure 9](#). No maintenance therapy will be used in this study.

8.1.8.2 Rituximab Investigational Product

Commercially available rituximab will be used as the standard of care therapy for follicular lymphoma unless institutional or regional regulations request otherwise.

The investigator shall take responsibility for and shall take all steps to maintain appropriate records and ensure appropriate supply, storage, handling, distribution and usage of trial treatments in accordance with the protocol and any applicable laws and regulations.

8.1.8.3 Rituximab Administration

For patients in Part 5, treatment will be administered beginning on Study Day 0 after all procedures and assessments have been completed.

Rituximab will be administered as a dose of 375 mg/m² IV infusion. Premedicate before each infusion with acetaminophen and an antihistamine or other appropriate premedication regimen as specified by local institutional guidelines. First Infusion: Initiate infusion at a rate of 50 mg/hr. In the absence of infusion toxicity, increase infusion rate by 50 mg/hr increments every 30 minutes, to a maximum of 400 mg/hr. Subsequent Infusions: Initiate infusion at a rate of 100 mg/hr. In the absence of infusion toxicity, increase rate by 100 mg/hr increments at 30-minute intervals, to a maximum of 400 mg/hr. Interrupt the infusion or slow the infusion rate for infusion reactions. Continue the infusion at one-half the previous rate upon improvement of symptoms.

8.1.8.4 Dose Modification, Warning and Precautions for Rituximab

Approved regulatory rituximab labeling and institutional guidelines for contraindications, warnings and precautions should be followed. Some of them are briefly summarized below.

Infusion Reaction

Rituxan can cause severe, including fatal, infusion reactions. Severe reactions typically occurred during the first infusion with time to onset of 30–120 minutes. Rituxan-induced infusion reactions and sequelae include urticaria, hypotension, angioedema, hypoxia, bronchospasm, pulmonary infiltrates, acute respiratory distress syndrome, myocardial infarction, ventricular fibrillation, cardiogenic shock, anaphylactoid events, or death.

Premedicate patients with an antihistamine and acetaminophen prior to dosing. Institute medical management (e.g., glucocorticoids, epinephrine, bronchodilators, or oxygen) for infusion reactions as needed. Depending on the severity of the infusion reaction and the required interventions, temporarily or permanently discontinue rituximab. Resume infusion at a minimum 50% reduction in rate after symptoms have resolved. Closely monitor the following patients: those with pre-existing cardiac or pulmonary conditions, those who experienced prior cardiopulmonary adverse reactions, and those with high numbers of circulating malignant cells ($\geq 25,000/\text{mm}^3$).

Tumor Lysis Syndrome

Acute renal failure, hyperkalemia, hypocalcemia, hyperuricemia, or hyperphosphatemia from tumor lysis, some fatal, can occur within 12–24 hours after the first infusion of rituximab in patients with NHL. A high number of circulating malignant cells ($\geq 25,000/\text{mm}^3$) or high tumor burden, confers a greater risk of TLS. Administer aggressive intravenous hydration and anti-hyperuricemic therapy in patients at high risk for TLS. Correct electrolyte abnormalities, monitor renal function and fluid balance, and administer supportive care, including dialysis as indicated.

Severe Mucocutaneous Reactions

Mucocutaneous reactions, some with fatal outcome, can occur in patients treated with rituximab. These reactions include paraneoplastic pemphigus, Stevens-Johnson syndrome, lichenoid dermatitis, vesiculobullous dermatitis, and toxic epidermal necrolysis. The onset of these reactions has varied from 1–13 weeks following rituximab exposure. Discontinue rituximab in patients who experience a severe mucocutaneous reaction. The safety of readministration of rituximab to patients with severe mucocutaneous reactions has not been determined.

Immune Design**G100 (GLA-SE) and Pembrolizumab or Rituximab****Protocol IMDZ-G142; Version 04B, November 15, 2018**

Progressive Multifocal Leukoencephalopathy (PML)

JC virus infection resulting in PML and death can occur in rituximab-treated patients with hematologic malignancies or with autoimmune diseases. The majority of patients with hematologic malignancies diagnosed with PML received rituximab in combination with chemotherapy or as part of a hematopoietic stem cell transplant. The patients with autoimmune diseases had prior or concurrent immunosuppressive therapy. Most cases of PML were diagnosed within 12 months of their last infusion of rituximab.

Consider the diagnosis of PML in any patient presenting with new-onset neurologic manifestations. Evaluation of PML includes, but is not limited to, consultation with a neurologist, brain MRI, and lumbar puncture. Discontinue rituximab in patients who develop PML.

Hepatitis B Virus (HBV) Reactivation

Hepatitis B virus (HBV) reactivation with fulminant hepatitis, hepatic failure, and death can occur in patients with hematologic malignancies treated with rituximab. The median time to the diagnosis of hepatitis was approximately 4 months after the initiation of rituximab and approximately one month after the last dose.

Screen patients at high risk of HBV infection before initiation of rituximab. Closely monitor carriers of hepatitis B for clinical and laboratory signs of active HBV infection for several months following rituximab therapy. Discontinue rituximab and any concomitant chemotherapy in patients who develop viral hepatitis, and institute appropriate treatment including antiviral therapy.

Infections

Serious, including fatal, bacterial, fungal, and new or reactivated viral infections can occur during and up to one year following the completion of rituximab-based therapy. New or reactivated viral infections included cytomegalovirus, herpes simplex virus, parvovirus B19, varicella zoster virus, West Nile virus, and hepatitis B and C. Discontinue rituximab for serious infections and institute appropriate anti-infective therapy.

Cardiovascular

Discontinue rituximab infusions for serious or life-threatening cardiac arrhythmias. Perform cardiac monitoring during and after all infusions of rituximab for patients who develop clinically significant arrhythmias, or who have a history of arrhythmia or angina.

Renal

Severe, including fatal, renal toxicity can occur after rituximab administration in patients with NHL. Renal toxicity has occurred in patients who experience tumor lysis syndrome and in patients with NHL administered concomitant cisplatin therapy during clinical trials. Monitor closely for signs of renal failure and discontinue rituximab in patients with a rising serum creatinine or oliguria.

Immunization

The safety of immunization with live viral vaccines following Rituxan therapy has not been studied and vaccination with live virus vaccines is not recommended.

Laboratory Monitoring

In patients with lymphoid malignancies, during treatment with rituximab, obtain complete blood counts (CBC) and platelet counts prior to each rituximab course.

Further details regarding the safety, dose, and dose adjustments of rituximab are reviewed in the product label ([Rituximab PI 2018](#))

8.1.9 Contraception

G100, rituximab and/or pembrolizumab may have adverse effects on a fetus in utero.

Furthermore, it is not known if G100 and/or pembrolizumab have transient adverse effects on the composition of sperm.

Subjects should be informed that taking the study medication may involve unknown risks to the fetus (unborn baby) if pregnancy were to occur during the study. Therefore, non-pregnant, non-breast-feeding FCBP may only be enrolled if they are willing to use 2 methods of birth control or are considered highly unlikely to conceive. Highly unlikely to conceive is defined as 1) surgically sterilized, or 2) postmenopausal (a woman who is ≥ 45 years of age and has not had menses for greater than 1 year will be considered postmenopausal), or 3) not heterosexually active for the duration of the study. Abstinence is only acceptable as “true abstinence” when it is in line with the preferred and usual lifestyle of the patient and not a periodic occurrence (see [Appendix F](#)). The two birth control methods can be either two barrier methods or a barrier method plus a hormonal method to prevent pregnancy. Subjects should start using birth control from study Visit 1 throughout the study period up to 120 days after the last dose of study therapy if receiving pembrolizumab or at least 90 days if only receiving G100.

The following are considered adequate barrier methods of contraception: diaphragm, condom (by the partner), copper intrauterine device, sponge, or spermicide as per local regulations or guidelines. Appropriate hormonal contraceptives will include any registered and marketed contraceptive agent that contains an estrogen and/or a progestational agent (including oral, SC,

intrauterine, or IM agents). See [Appendix F](#) for additional details and definitions of highly effective agents.

For male patients, acceptable contraception includes documented sterility such as what is achieved following surgical sterilization (vasectomy or orchiectomy) or use of male condom. If the partner is a woman of childbearing potential, supplemental contraception with hormonal or barrier methods should be considered.

In order to participate in the study, subjects must adhere to the contraception requirement (described above) for the duration of the study and during the follow-up period defined in [Section 12.7](#). If there is any question that a subject will not reliably comply with the requirements for contraception, that subject should not be entered into the study.

8.1.10 Use in Pregnancy

If a subject inadvertently becomes pregnant while on treatment with G100, rituximab and/or pembrolizumab, the subject will immediately be removed from the study. The site will contact the subject at least monthly and document the subject's status until the pregnancy has been completed or terminated. The outcome of the pregnancy will be reported to the Sponsor without delay and within 24 hours if the outcome is a serious adverse experience (e.g., death, abortion, congenital anomaly, or other disabling or life-threatening complication to the mother or newborn). The study investigator will make every effort to obtain permission to follow the outcome of the pregnancy and report the condition of the fetus or newborn to the Sponsor. If a male subject impregnates his female partner the study personnel at the site must be informed immediately and the pregnancy reported to the Sponsor and followed as described above and in [Section 12.7](#).

8.1.11 Use in Nursing Women

It is unknown whether G100, rituximab and/or pembrolizumab is excreted in human milk. Since many drugs are excreted in human milk, and because of the potential for serious adverse reactions in the nursing infant, subjects who are breast-feeding are not eligible for enrollment.

8.2 Subject Withdrawal/Discontinuation Criteria

8.2.1 Discontinuation of Study Therapy after Complete Response (CR)

Discontinuation of treatment may be considered for subjects who have attained a confirmed CR that have been treated for at least 24 weeks with pembrolizumab and had at least 2 treatments with pembrolizumab beyond the date when the initial CR was declared.

For patients receiving pembrolizumab who experience grade 2 pneumonitis, the patient should be discontinued from study treatment but continued to be monitored.

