6.5 Dosing Delays / Dose Modifications

There are no adjustments for dose delay for a given patient, and treatment delays of >14 days from the treatment plan will not be allowed. If a patient experiences a DLT, treatment of that patient will be suspended. A subject may be considered for receiving further injections of the G100 investigational drug product on a case-by-case basis after the PI and medical monitor, in consultation with the independent DMC, have evaluated the risk/benefit ratio for a subject. As an example, for subjects who have experienced a tumor response and had a non-life- and non-organ-threatening DLT, continuation of treatment as per protocol may be considered.

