8.1.5.5 Dose Modification for Pembrolizumab

AEs associated with Pembrolizumab exposure may represent an immunologic etiology. These immune-related AEs (irAEs) may occur shortly after the first dose or several months after the last dose of Pembrolizumab treatment and may affect more than one body system simultaneously. Therefore, early recognition and initiation of treatment is critical to reduce complications. Based on existing clinical study data, most irAEs were reversible and could be managed with

Immune Design**G100 (GLA-SE) and Pembrolizumab or Rituximab****Protocol IMDZ-G142; Version 04B, November 15, 2018**

interruptions of Pembrolizumab, administration of corticosteroids and/or other supportive care. For suspected irAEs, ensure adequate evaluation to confirm etiology or exclude other causes. Additional procedures or tests such as bronchoscopy, endoscopy, skin biopsy may be included as part of the evaluation. Based on the severity of irAEs, withhold or permanently discontinue Pembrolizumab and administer corticosteroids. Dose modification and toxicity management guidelines for irAEs associated with Pembrolizumab are provided in [Table 3](#).

Immune Design**G100 (GLA-SE) and Pembrolizumab or Rituximab****Protocol IMDZ-G142; Version 04B, November 15, 2018****Table 3: Dose Modification and Toxicity Management Guidelines for Immune-related AEs Associated with Pembrolizumab**

General instructions:				

 1. Corticosteroid taper should be initiated upon AE improving to Grade 1 or less and continue to taper over at least 4 weeks. 2. For situations where Pembrolizumab has been withheld, Pembrolizumab can be resumed after AE has been reduced to Grade 1 or 0 and corticosteroid has been tapered. Pembrolizumab should be permanently discontinued if AE does not resolve within 12 weeks of last dose or corticosteroids cannot be reduced to ≤ 10 mg prednisone or equivalent per day within 12 weeks. 3. For severe and life-threatening irAEs, IV corticosteroid should be initiated first followed by oral steroid. Other immunosuppressive treatment should be initiated if irAEs cannot be controlled by corticosteroids. 				
Immune-related AEs	Toxicity grade or conditions (CTCAEv4.0)	Action taken to Pembrolizumab	irAE management with corticosteroid and/or other therapies	Monitor and follow-up

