Pneumonitis	Grade 2	Withhold	Administer corticosteroids (initial dose of 1-2 mg/kg prednisone or equivalent) followed by taper	Monitor participants for signs and symptoms of pneumonitis Evaluate participants with suspected pneumonitis with radiographic imaging and initiate corticosteroid treatment Add prophylactic antibiotics for opportunistic infections
	Grade 3 or 4, or recurrent Grade 2	Permanently discontinue		
Diarrhea / Colitis	Grade 2 or 3	Withhold	Administer corticosteroids (initial dose of 1-2 mg/kg prednisone or equivalent) followed by taper	Monitor participants for signs and symptoms of enterocolitis (i.e., diarrhea, abdominal pain, blood or mucus in stool with or without fever) and of bowel perforation (i.e., peritoneal signs and ileus). Participants with \geq Grade 2 diarrhea suspecting colitis should consider GI consultation and performing endoscopy to rule out colitis. Participants with diarrhea/colitis should be advised to drink liberal quantities of clear fluids. If sufficient oral fluid intake is not feasible, fluid and electrolytes should be substituted via IV infusion.
	Grade 4	Permanently discontinue		
AST / ALT elevation or Increased bilirubin	Grade 2	Withhold	Administer corticosteroids (initial dose of 0.5-1 mg/kg prednisone or equivalent) followed by taper	Monitor with liver function tests (consider weekly or more frequently until liver enzyme value returned to baseline or is stable)
	Grade 3 or 4	Permanently discontinue	Administer corticosteroids (initial dose of 1-2 mg/kg prednisone or equivalent) followed by taper	

Immune Design**G100 (GLA-SE) and Pembrolizumab or Rituximab****Protocol IMDZ-G142; Version 04B; November 15, 2018**

Type 1 diabetes mellitus (T1DM) or Hyperglycemia	Newly onset T1DM or Grade 3 or 4 hyperglycemia associated with evidence of β -cell failure	Withhold	Initiate insulin replacement therapy for participants with T1DM Administer anti-hyperglycemic in participants with hyperglycemia	Monitor participants for hyperglycemia or other signs and symptoms of diabetes.
Hypophysitis	Grade 2	Withhold	Administer corticosteroids and initiate hormonal replacements as clinically indicated.	Monitor for signs and symptoms of hypophysitis (including hypopituitarism and adrenal insufficiency)
	Grade 3 or 4	Withhold or permanently discontinue ¹		
Hyperthyroidism	Grade 2	Continue	Treat with non-selective beta-blockers (e.g., propranolol) or thionamides as appropriate	Monitor for signs and symptoms of thyroid disorders.

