10.1 Visit Windows

The treatment windows below apply unless otherwise specified in the study procedures that there is a different event window. For Visit 1, in Parts 1, 2, 3, 4, and 5 all screening procedures will have the windows of Days -30 to -1. For Visit 2, in Parts 1 and 2, screening procedures will have windows of Days -7 to -1; for Visit 2, in Part 3, 4, and 5 a window of Days -14 to -1 will apply, except as otherwise specified in the procedures. All dosing-treatment visits will have a window of \pm 2 days from the day specified. After completion of G100 treatment, follow-up visits will have a window of \pm 1 week (7 days). Following the Day 77 EOS Visit, patients receiving pembrolizumab will have a window of \pm 5 days for pembrolizumab dose administration and will have a window of \pm 14 days for restaging radiographic studies. If a dose interruption beyond the windows listed above is required, this should be discussed and approved by the medical monitor; treatment delays of >14 days from the treatment plan will not be allowed.

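### For a first Grade 2 pneumonitis, Protocol 8.2.1 discontinues study treatment with no stated route back, while Table 3 withholds pembrolizumab and allows it to resume

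*Protocol*

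**What the plan says.** **Section 8.2.1.** "For patients receiving pembrolizumab who experience grade 2 pneumonitis, the patient should be discontinued from study treatment but continued to be monitored". The sentence is the last in a subsection on stopping therapy after complete response, within the Section 8.2 withdrawal and discontinuation criteria.

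**Table 3 (Section 8.1.5.5).** The pneumonitis row gives Withhold for Grade 2. It gives permanent discontinuation for "Grade 3 or 4, or recurrent Grade 2". The general instructions above the table add three things:

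- Resumption: "For situations where Pembrolizumab has been withheld, Pembrolizumab can be resumed after AE has been reduced to Grade 1 or 0", once the corticosteroid has been tapered.
- Taper: "Corticosteroid taper should be initiated upon AE improving to Grade 1 or less and continue to taper over at least 4 weeks".
- Outer limit: "Pembrolizumab should be permanently discontinued if AE does not resolve within 12 weeks of last dose", or if steroids cannot be brought down to 10 mg prednisone a day or less in the same period.

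**Which rule sites are sent to.** Section 6.1 says that pembrolizumab dose changes for attributed adverse events follow the product guidelines and the protocol. Section 8.1.6 refers sites to Table 3 "for guidelines regarding dose modification and supportive care", and applies that guidance to events judged related to pembrolizumab.

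**Delay limits.** Section 6.5 says "treatment delays of >14 days from the treatment plan will not be allowed". Section 10.1 sets the pembrolizumab dosing window after Day 77 and continues "If a dose interruption beyond the windows listed above is required, this should be discussed and approved by the medical monitor". It then closes the paragraph with the same 14-day limit.

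**The concern.** An investigator whose patient has a first Grade 2 pneumonitis finds two current instructions. Under Table 3 the patient may be re-exposed to pembrolizumab after recovery. Under Section 8.2.1 the patient has been discontinued and is only monitored. Re-exposure after an immune-related lung event is a safety decision and should have one answer. Section 8.4.2 requires discussion with the Medical Monitor before therapy continues after systemic steroids, but no text tells the monitor which rule governs.

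The two texts also differ in reach. Section 8.2.1 speaks of study treatment, which Section 6.2 uses for G100, pembrolizumab or rituximab. Table 3 acts on pembrolizumab alone. Read literally, 8.2.1 stops G100 as well.

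There is a small reporting effect. SAP Section 5.7.2 counts events leading to interruption and events leading to discontinuation separately, so the same event changes row with the rule applied.

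**Working it through.** **Step 1: the two rules side by side.**

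| Question | Section 8.2.1 | Table 3 |
|---|---|---|
| Immediate action at Grade 2 | Stop | Stop (withhold) |
| First versus recurrent event | Not distinguished | First: withhold; recurrent: permanent stop |
| Route back | None stated | At Grade 0-1, after steroid taper |
| What is stopped | Study treatment | Pembrolizumab |
| Related events only | Not stated | Yes (Section 8.1.6) |

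The rules agree on the first row. They part on rechallenge after a first event and on G100.

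**Step 2: the delay that Table 3 implies.** The protocol states no figure for this, so there is none to reproduce. Inputs:

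- Dosing interval 21 days (every 3 weeks; Section 10.3.22.1).
- Minimum taper 28 days, starting at improvement to Grade 0-1 (Table 3).
- d = days from the last pembrolizumab dose to that improvement.
- Assumptions: the taper must be complete before restart, and delay is counted from the planned dose day.

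Earliest restart = d + 28 days after the last dose.

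Minimum delay = (d + 28) − 21 = d + 7 days.

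The 14-day cap is met only if d + 7 ≤ 14, that is d ≤ 7.

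| d (days) | Minimum delay (days) | Within 14 days? |
|---|---|---|
| 3 | 10 | Yes |
| 7 | 14 | Yes |
| 8 | 15 | No |
| 14 | 21 | No |

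On these assumptions, a hold that follows Table 3 stays inside the cap only when the pneumonitis both appears and improves within 7 days of the last dose.

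**Step 3: whether the cap reaches pembrolizumab.**

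- Section 8.1.4 places a two-week limit directly after its rule on holding G100 injections. That limit is about G100.
- Section 6.5 goes on to discuss further G100 injections, so it is probably about G100 too.
- Section 10.1 names no drug in the cap, but the cap ends the paragraph that sets the pembrolizumab windows. This is the only place with a plausible reach to pembrolizumab.
- Section 8.1.5.6 gives 3 weeks (21 days) for returning after unrelated pembrolizumab interruptions, which is 7 days more than the cap. This suggests the cap was not meant for pembrolizumab, but no text says so.

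**The case against.** The best reply is that this is a stray sentence and practice would follow Table 3. Section 8.2.1 does not say permanently, whereas Tables 3 and 4 use that word when they mean it. For rituximab, Section 8.1.8.4 speaks of discontinuing either temporarily or permanently, so the bare verb can include a pause. Sections 6.1 and 8.1.6 lead to Table 3, and drug-specific rules normally govern over general visit windows.

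Much of this stands. That 8.2.1 forbids a restart is an inference, and Table 3 is the likelier rule. But the sentence sits among withdrawal criteria, offers no resumption, and sets stopping treatment against continued monitoring. Table 3 itself, in its row for other immune-related events at Grade 3, treats withholding and discontinuing as alternatives. Neither cross-reference is a precedence clause. Probable intent is what a correction should put in writing.

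Three stronger readings are tempting and are not supported:

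- **A maximum delay of 63 days, 4.5 times the cap.** A reader might take 12 weeks as the latest restart (84 − 21 = 63; 63/14 = 4.5). Day 84 is a deadline for resolution and steroid reduction, not for restart, so 63 is not an upper bound.
- **A changed dose-limiting toxicity count.** A reader might infer that stopping under 8.2.1 meets criterion 7 of Section 6.2 while a Table 3 hold does not. Cycle 1 is undefined, and criteria 6 and 9, on delayed or missed dosing, could capture a hold as well. The effect cannot be determined.
- **A protocol-wide 14-day conflict.** The limit is about G100 in 8.1.4 and probably in 6.5. Only 10.1 needs clarifying.

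**Conclusion.** The contradiction is real and limited. For a first Grade 2 pneumonitis the protocol stops pembrolizumab at once under either text, so a reader who infers that a patient might be kept on drug during the event would be wrong. What is unsettled is whether rechallenge is allowed and whether G100 continues. The open delay cap in Section 10.1 is a secondary ambiguity. Its size, d + 7 days against 14, rests on a completed taper before restart. If reduction to 10 mg prednisone a day is enough, restart could come sooner.

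The scope is mainly Part 4, with 22 planned efficacy evaluable patients and up to 12 more if escalation continues beyond them. Section 6.1 already describes Part 2 combination results. No pneumonitis rate is given, so the number of patients affected cannot be stated. No sample size, error rate or endpoint definition changes. SAP Section 9 records that the sponsor terminated the study, so the practical use may now be in reporting. A correction is still worthwhile because a safety rule is inconsistent as written and costs almost nothing to put right.

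**What to change.** 1. Replace the pneumonitis sentence in Section 8.2.1 with: *Manage pneumonitis per Table 3: withhold pembrolizumab for a first Grade 2 event; permanently discontinue for Grade 3-4 or recurrent Grade 2.* State whether G100 continues meanwhile. If the stricter rule was intended, change the Grade 2 entry in Table 3 to permanent discontinuation.
2. Add to Section 10.1 that the 14-day limit does not apply to pembrolizumab withheld under Table 3 or interrupted under Section 8.1.5.6.
3. If dosing has ended, state in the clinical study report which rule was applied to any Grade 2 pneumonitis.

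The cost is two or three sentences in a clarification letter or protocol correction, or one sentence in the report.
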